8.4 Screening for Eligibility

After the patient gives permission to review her/his medical/research records, the study staff member will screen for eligibility by examining the medical records to confirm that the patient initiated ART containing tenofovir within the last 4 months and record the most recent VL value and date of draw.

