12. STATISTICAL CONSIDERATIONS

12.1. Overview and General Design Issues

For Aim 2, we will explore whether providing adherence feedback to patients and providers results in changes to patient adherence behavior (as measured by TFV-DP levels, VL, Wisepill use patterns, and self-report) and/or provider behavior with respect to patient management (e.g., requests for additional laboratory tests, calling patient back for an additional appointment, referring patient to an adherence counselor, referring patient to the 'risk of treatment failure clinic'). Below we describe the analytical plan to assess change in patient adherence behavior using Wisepill openings as an example.

This 5-month pilot with a small sample size, will provide preliminary estimates that can be used to inform future power calculations and the design of a larger trial (e.g., estimates of effect size, interclass correlation [ICC] for within individual and within provider/clinic correlation). Using Aim 1 data on self-reported adherence, which includes about 3,000 observations, the mean adherence is 81.96% with a standard deviation of 11.42%. The current plan to recruit 60 subjects and collect their monthly adherence data over the subsequent 4-month period will result in 180 change scores (90 per group) for the Aim 2 analysis. Using the estimated standard deviation from our existing data and assuming the ICC between successive change scores is no greater than 0.20, we will be able to detect a 5.59 percentage point difference in ART adherence between the intervention and control group with 80% power. Assume the mean adherence is about 80% for the control group (very close to what we observed from our observational study in Aim 1), if in truth, the mean adherence is 85.59% (which we optimistically believe is achievable), we have 80% probability to declare the difference of adherence between intervention and control is statistically significant. Therefore, we believe that the data we will collect from 60 participants over the 4-months of follow up will provide adequate power to achieve the study goal.

To generate preliminary estimates of the effect of giving feedback on adherence behavior, we will compare change in average percentage of Wisepill openings (for example) from one month to the next between Feedback and No Feedback (Control) participants.

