Because feedback begins at the first return visit at Month 1 after baseline, each Feedback Group participant will provide up to three change score outcomes (for month $i-1$ to month i for $i=2,3,4$). We will compare these to the corresponding change scores in the Control Group in a generalized linear model (GLM) using generalized estimating equations (GEE) to account for within-subject correlation (ICC) among their three change-scores. The analysis model will include a constant term and the group indicator.

With the limited pilot sample size of 60, we will be able to detect moderately large effects on average improvement in adherence. For example, if the ICC between successive change scores is no greater than 0.20, then the detectable standardized mean difference will be $2.8 * [(2/30) * (1 + 0.2 * (3-1))]^{1/2} = 0.86$, a "large" effect.

Given that this is a pilot study, our ability to explore the role of the moderating variables on adherence-related behavior will be limited. However, looking at the monthly change-scores can reveal important features on which to focus. Moreover, the larger Aim 1 sample (N=250) will provide key data on individual and structural factors affecting adherence, retention, and preferences for sample collection and feedback that we will utilize in multivariable analyses as predictors of DBS TFV-DP levels and Wisepill use patterns. We will also examine these factors as potential effect modifiers in Aim 1 analyses.

For providers we will examine changes in clinical management patterns, for example requests for additional tests or adherence counselling sessions usually only triggered by a raised VL.

Similar to Aim 1, the Baseline and Visit 4 (last visit) Quantitative Assessments will cover a large array of participant information and behaviors that could be potential confounders. To examine how potential confounding factors can influence our statistical analysis, we will first identify a list of variables that is possible be candidates for potential confounding factors and then test whether any of those variables is associated with our outcome (i.e., adherence) and exposure (i.e., the intervention) in our sample. If found, we will include them in the primary analysis model to obtain the adjusted intervention effect. While the official primary analysis will be the one without covariate adjustment, the adjusted analysis will help to interpret the findings from primary analysis.

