12.4. Randomization/Blinding Procedures/Unblinding Procedures

Participants in the pilot study will be randomized 1:1 to either Feedback Group (N=30) or No Feedback (Control) Group (N=30) by study staff using a randomization list generated by the study Biostatistician ([name]). The study will not be blinded.

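### The official primary model leaves out the Month 1 value of the measure analysed, which is already collected; pre-specifying it as a covariate would gain precision at small cost

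*Combined protocol and SAP*

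**What the plan says.** Section 12.1 uses Wisepill openings as its worked example. Changes run from Month 1 to 2, 2 to 3 and 3 to 4, and "each Feedback Group participant will provide up to three change score outcomes". These are compared with the control arm's changes by GEE. On the content of the model: "The analysis model will include a constant term and the group indicator". The status of that model is also stated: "While the official primary analysis will be the one without covariate adjustment".

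An adjusted analysis is planned in a supporting role. Candidates come from the Baseline and Visit 4 Quantitative Assessments and are tested for association with both adherence and study arm: "If found, we will include them in the primary analysis model to obtain the adjusted intervention effect". No covariate is named in advance.

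The values needed for adjustment are already collected. DBS and self-report are taken at every visit (Sections 9.7.4 and 9.9.1.1). Wisepill is dispensed at baseline (Section 9.8.1), which gives one month of data before the Month 1 visit. At screening, staff "record the most recent VL value and date of draw" (Section 8.4). Section 12.4 states no stratification: "Participants in the pilot study will be randomized 1:1 to either Feedback Group (N=30) or No Feedback (Control) Group (N=30").

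**The concern.** Change from a starting month usually depends on the starting level: people who begin low tend to rise, and people who begin high tend to fall. A change score subtracts the starting value in full. If the true slope of the later value on the starting value is below 1, that over-corrects, and a chance difference between 30 and 30 in Month 1 adherence moves the estimated effect the opposite way. Adding the Month 1 value to the model removes that part of the variation.

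The supporting adjusted analysis does not repair this. A covariate enters only if it is associated with arm as well as outcome. In a randomised trial association with arm is chance, so a strongly prognostic but balanced covariate would be left out. Visit 4 candidates are also measured after feedback and may be affected by it.

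At stake is the precision of the effect estimate. Section 12.1 says the pilot is meant to supply such estimates for the design of a larger trial.

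**Working it through.** **Inputs from Section 12.1.** 30 per arm; three change scores each ("will result in 180 change scores (90 per group) for the Aim 2 analysis"); SD 11.42 points from Aim 1 self-report ("the mean adherence is 81.96% with a standard deviation of 11.42" percent); correlation of successive changes at most 0.20; detectable difference 5.59 points at 80% power, and separately 0.86 SD.

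**Reproducing the plan's figures.** With multiplier 1.960 + 0.842 = 2.80 and design effect 1 + 0.2 × 2 = 1.4:
- In points: 2.80 × 11.42 × √[(2/90) × 1.4] = 5.64, against the stated 5.59.
- Standardised: 2.8 × √[(2/30) × 1.4] = 0.855, against the stated 0.86.

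Both reproduce, although they disagree with each other (5.59/11.42 = 0.49 SD, not 0.86). That is a separate matter. The variance ratios below apply to either.

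**What the unadjusted model estimates.** With complete data and an independence or exchangeable working correlation, the group coefficient is the between-arm difference in the mean of three changes:

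[(Y2 − Y1) + (Y3 − Y2) + (Y4 − Y3)]/3 = (Y4 − Y1)/3.

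**Effect of adding Y1.** Take equal variances and let r be the Month 1 to Month 4 correlation. The variance of Y4 − Y1 is proportional to 2(1 − r). After adjusting for Y1 it is proportional to 1 − r². The ratio is

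(1 − r²)/[2(1 − r)] = (1 + r)/2.

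Under constant correlation ρ, r = ρ. Under AR(1), Months 1 and 4 are three steps apart, so r = ρ³. Estimating one extra coefficient with N = 60 costs a factor of about 1 + 1/(60 − 4) = 1.018. ρ is assumed, because the documents give none.

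| Pattern | ρ | (1 + r)/2 | × 1.018 | 5.59 × √ratio |
|---|---|---|---|---|
| Constant | 0.3 | 0.650 | 0.662 | 4.55 |
| Constant | 0.5 | 0.750 | 0.763 | 4.88 |
| Constant | 0.7 | 0.850 | 0.865 | 5.20 |
| Constant | 0.8 | 0.900 | 0.916 | 5.35 |
| Constant | 0.9 | 0.950 | 0.967 | 5.50 |
| AR(1) | 0.5 | 0.563 | 0.573 | 4.23 |
| AR(1) | 0.7 | 0.672 | 0.683 | 4.62 |
| AR(1) | 0.8 | 0.756 | 0.769 | 4.90 |

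Simulation of 4,000 trials with 30 per arm gave ratios of 0.68, 0.78, 0.87 and 0.92 (constant 0.3, 0.5, 0.7, 0.8) and 0.58, 0.70 and 0.76 (AR(1) 0.5, 0.7, 0.8). These lie within about 0.02 of the formula. Mean estimates with and without adjustment agreed to about 0.01.

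The last column only shrinks the plan's own number in proportion; it is not a forecast. The plan's 5.59 uses an SD of levels and a positive correlation of changes, whereas under constant correlation adjacent changes correlate at −0.5.

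**Visit 0 instead of Month 1.** Visit 0 is not part of (Y4 − Y1)/3. Under constant correlation, cov(Y0, Y4 − Y1) is proportional to ρ − ρ = 0, so there is no gain; simulation gave a ratio of 1.02. Under AR(1) the share of variance explained is (ρ − ρ⁴)²/[2(1 − ρ³)] = ρ²(1 − ρ³)/2, which is 0.11, 0.16 and 0.16 at ρ = 0.5, 0.7 and 0.8.

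**Downside.** One uninformative covariate adds about 1.8% to the variance. Two add 2/(60 − 5) = 3.6%, which lowers power at 5.59 points from 79.3% to 77.8%.

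**The case against.** An unadjusted primary analysis with a supporting adjusted one is valid. This is a small pilot, the Wisepill model is offered as an example, and the outcome already subtracts the starting value. The correlations above are assumptions; at constant correlation 0.8 the gain is about 8%, which changes little. All of that stands. It limits the size of the point but gives no reason to leave the covariate out.

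Several stronger readings are tempting, and the documents do not support them:

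- *The unadjusted estimate is biased by chance imbalance.* It is not. Under randomisation the imbalance is already reflected in the standard error, and adjustment does not shift the expected estimate. Lost precision and exposure to imbalance are the same variance and should be counted once.
- *Adjustment is free.* It is cheap. Besides the 2% per uninformative covariate, complete-case adjustment would drop every later change of a participant with no Month 1 Wisepill value, where the unadjusted model loses only the first. Sections 9.8 and 13.5 foresee device problems.
- *Any baseline value gives the same gain.* The 8–42% belongs to Month 1 alone.
- *The last clinic viral load should be in the model because imbalance is likely.* If 12 of 60 are unsuppressed (the 20% implied by Section 8.1.1), an 8:4 or worse split has a 33% chance and 9:3 or worse 10%. That describes imbalance in viral load status, not error in a change-score estimate. The documents give no correlation between the two, and routine viral load is annual (Section 9.9.1.3), so the value may be months old.

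One reservation concerns Month 1 itself. Section 9.3 sends results to Feedback-arm providers before the monthly visit, so the Month 1 value may not be strictly free of feedback. The plan's change score starts from the same value, so the unadjusted analysis shares the problem.

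**Conclusion.** The point holds as a loss of precision. The official model ignores a starting value that the trial collects anyway, and the supporting analysis selects covariates in a way that does not recover it. The expected variance reduction is about 8–32% under constant correlation (0.8 to 0.3) or 24–42% under AR(1) (0.8 to 0.5), tending to nil as the correlation approaches 1. The figures assume equal variances over time, complete data, an independence or exchangeable working correlation, and a continuous outcome. The true correlation is not in the documents; Aim 1 data could supply one for TFV-DP and self-report. No gain can be put on the last clinic viral load.

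**What to change.** Amend Section 12.1 as follows:

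1. Make the official primary model the same GEE with group plus the Month 1 value of the measure analysed (Wisepill, TFV-DP or self-report), named in advance. Keep the model without covariates as a sensitivity analysis.
2. Remove selection of primary-model covariates by testing association with arm, and exclude Visit 4 variables as candidates.
3. State whether provider feedback before the Month 1 visit could affect the Month 1 value. Only if it is judged to do so, use Visit 0 TFV-DP and self-report as the fallback, accepting the smaller or absent gain.
4. Give a rule for a missing Month 1 Wisepill value that keeps the later changes, for example imputing the covariate without reference to arm.
5. Treat last clinic viral load status as an optional second covariate.
6. Handle a binary viral load outcome separately: with a logit link, adjustment changes the effect being estimated.

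The cost is wording in the analysis plan and one degree of freedom, or two with the optional covariate. No visit, assay or form changes.

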12.2 Study Endpoints

12.2.1 Primary Endpoint

Our primary endpoint is defined as behaviors in response to the receipt of information about TFV-DP drug levels. Behavioral responses will be assessed (and explored) by subsequent TFV-DP levels, subsequent VL(s), Wisepill use, self-reported medication adherence, and responses to interview questions in the Exit Interviews with patient participants, and provider FGDs.

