6. OBJECTIVES

6.1. Primary Objectives

The primary objectives of this study are to (a) determine the feasibility of giving patients and providers monthly feedback about TFV-DP levels and (b) examine patient and provider behaviors in response to receiving this information, specifically patient medication adherence as measured with Wisepill, and clinical management of patients.

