9.7.3. Exit interview

Study staff will administer a semi-structured Exit Interview during the Visit 4 Quantitative Assessment to all study participants. Feedback arm participants will be asked about their understanding and perceptions of the meaning of the drug-level feedback, whether (and if so how) the feedback from the study staff and/or providers influence participants' behavior (e.g., medication-taking, disclosure to people in their social network, seeking adherence support, etc.). No feedback arm participants will be asked about if/how they would like to receive feedback if this was put into routine clinical practice (e.g., from a lay HCW, from a doctor, by SMS).

In both cases, the Exit Interview assessment will include closed and open-ended questions exploring the patient's thoughts about receiving DBS-based feedback.

9.7.4. Self-Reported Adherence Questionnaire.

Study staff will assess self-reported adherence in the past 30 days at every visit. The Self-Reported Adherence Questionnaire will take approximately 3 minutes to complete.

9.7.5. Pregnancy Status.

At each study visit, study staff will ask study participants (women only) whether they are currently pregnant or plan to become pregnant.

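### The primary endpoint lists six unranked sources, while the objective names Wisepill adherence and clinical management; nothing says which measure carries the significance statement

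*Combined protocol and SAP*

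**What the plan says.** **Objective.** Section 6.1 has two parts. Part (a) is to "determine the feasibility of giving patients and providers monthly feedback about TFV-DP levels". Part (b) concerns behaviour, "specifically patient medication adherence as measured with Wisepill, and clinical management of patients". The Protocol Summary (section 4) names the same two measures for (b).

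**Endpoint.** Section 12.2.1 and the summary read the endpoint from six sources: "Behavioral responses will be assessed (and explored) by subsequent TFV-DP levels, subsequent VL(s), Wisepill use, self-reported medication adherence, and responses to interview questions", given in participant exit interviews and provider focus groups. Neither place ranks them or gives a time point, summary measure or success rule.

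**Hypothesis.** Sections 5.3 and 12.3 list the same six sources as the evidence of improved adherence.

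**Analysis.** Section 12.1 introduces its model thus: "Below we describe the analytical plan to assess change in patient adherence behavior using Wisepill openings as an example". Its power calculation starts from a different measure ("Using Aim 1 data on self-reported adherence") and concludes that "we have 80% probability to declare the difference of adherence between intervention and control is statistically significant". The only feature fixed as officially primary is that the model has no covariate adjustment. Section 12.7.2, headed as the analysis plan, is marked not applicable. No alpha level or multiplicity rule is stated.

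**Clinical management.** Section 9.5 provides for chart review at each follow-up visit and after the study, and section 12.1 says management patterns will be examined. Chart review is not in the endpoint list.

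**The concern.** The endpoint and the objective it serves name different things. Wisepill is in both. Clinical management is in the objective, but its main instrument is missing from the endpoint. TFV-DP, viral load and self-report are in the endpoint, but objective (b) does not name them.

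A significance statement needs a named outcome, and here Wisepill has the objective, self-report has the power calculation, and TFV-DP and viral load have equal standing in the endpoint. The measures can disagree. By the protocol's own account TFV-DP reflects the prior 6 to 8 weeks (section 5.1.3) and Wisepill the past month (section 9.8). About 80% of participants are expected to be virally suppressed on their last routine result (section 8.1.1). Self-report comes from participants in an unblinded study (section 12.4). A lead measure chosen after the data are seen would weaken both a significance claim and the effect estimate passed on to the larger trial.

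The hypothesis also relies on two sources that cannot test it. Feedback participants are asked how feedback affected them, whereas "No feedback arm participants will be asked about if/how they would like to receive feedback if this was put into routine clinical practice" (section 9.7.3). The focus groups are held with providers. Neither gives a between-arm contrast in adherence.

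**Working it through.** **1. The plan's own figure (section 12.1).** Inputs: SD 11.42 points (Aim 1 self-report), 90 change scores per group (3 for each of 30 participants), ICC 0.20, power 80%. The design effect is 1 + 0.20 × (3 − 1) = 1.4.

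- Standard error: 11.42 × √(2/90 × 1.4) = 11.42 × 0.1764 = 2.014 points.
- Detectable difference, one two-sided 5% test: (1.960 + 0.842) × 2.014 = 5.64 points, against 5.59 stated.
- Power at 5.59 points: 5.59/2.014 = 2.775; Φ(2.775 − 1.960) = 79.3%, against 80% stated.
- A one-sided 5% test would give (1.645 + 0.842) × 2.014 = 5.01 points, which does not fit.

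So the stated power corresponds to one outcome tested at two-sided 5%. The multiplier 2.8 in the second calculation of section 12.1 implies the same (1.96 + 0.84). That calculation gives 0.86 SD, or 0.86 × 11.42 = 9.8 points, which does not agree with 5.59. That is a separate matter and is not used here.

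**2. Four measures, each at two-sided 5%.** If independent:

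- at least one false result favouring feedback: 1 − 0.975⁴ = 9.6%
- at least one false result in either direction: 1 − 0.95⁴ = 18.5%

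The documents give no correlations between the measures. Simulating four equally correlated normal test statistics (1,000,000 draws) gives:

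| Assumed correlation | Favouring feedback | Either direction |
|---|---|---|
| 0.3 | 8.7% | 17.4% |
| 0.5 | 7.8% | 15.6% |
| 0.7 | 6.6% | 13.1% |
| 0.9 | 4.7% | 9.4% |

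A single two-sided 5% test gives 2.5% and 5%.

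**3. Keeping all four primary with Bonferroni.** Alpha is 0.05/4 = 0.0125 each, critical value 2.498.

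- Power at 5.59 points: Φ(2.775 − 2.498) = 60.9%.
- Detectable difference: (2.498 + 0.842) × 2.014 = 6.73 points.

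**4. Wisepill as the single endpoint.** Alpha stays at 5%, but 11.42 is a self-report SD and no Wisepill SD is given. The detectable difference is 5.64/11.42 = 0.494 times the SD: 5.64 points if 11.42 carries over, 0.494 × 15 = 7.4 points at an assumed SD of 15, and 0.494 × 20 = 9.9 points at an assumed 20.

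**The case against.** **This is a pilot.** Section 12.1 speaks of exploring and of preliminary estimates for a larger trial, and section 12.2.1 itself says the responses will be explored. The significance language is one conditional sentence illustrating power. This lowers the seriousness of the point. It does not remove it, because the same section claims adequate power and the probability it quotes must belong to some outcome. Deleting the sentence and reporting estimates only would settle the error-rate question, but the endpoint would still not match the objective.

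**Wisepill is already the lead measure in all but name.** The objective names it, section 9.8 defines it and section 12.1 works through it. This is a fair reading of intent, and it is why the fix costs little. But the analysis text calls it an example and the endpoint gives it no priority.

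**Three stronger readings a reader might infer are not supported.**

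- *That success on any one of four measures would confirm the hypothesis.* No success rule is written, and sections 5.3 and 12.3 join the measures with a conjunction. The gap is the absence of a rule.
- *That provider behaviour has no assessment.* The focus groups ask providers what they changed (section 9.6), chart review is scheduled (section 9.5), and section 12.1 says management patterns will be examined. What is missing is chart review in the endpoint list.
- *That interviews and focus groups are treated as confirmatory tests.* Section 12.1 already makes the content analysis of open-ended material exploratory, and both arms answer closed and open questions on drug-level feedback. The fault is confined to listing these sources in the endpoint and as evidence of improved adherence.

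**Wisepill is an imperfect choice.** Section 14.10 says it records openings, not ingestion, and can err in either direction. That stands as a limitation of following the sponsor's own objective.

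**Conclusion.** The point holds. The endpoint in section 12.2.1 and the summary does not match objective (b). No ranking, alpha or success rule identifies the measure behind the significance statement, chart review is analysed but not listed, and the hypothesis counts two sources that give no adherence contrast between arms.

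Because the hypothesis is directional, the relevant size is the chance of a false result favouring feedback: 9.6% for four independent tests and about 7.8% at correlation 0.5, against 2.5% for one test. The 18.5% figure counts false results in both directions under independence, so it should not be read as the chance of a falsely positive trial. Four measures of the same pill-taking are unlikely to be independent. All these figures assume that each measure is tested at two-sided 5%, which the plan does not say, and the correlations are assumed. The 80% power figure fits one test only; split over four by Bonferroni it would be 60.9%.

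This should be corrected, but the exploratory setting means that it does not undermine the study.

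**What to change.** 1. In section 12.2.1 and the summary, name Wisepill-measured adherence as the single primary adherence endpoint: the month-to-month change in percentage of openings, analysed by the GEE model of section 12.1 and tested at two-sided 5%. Remove the phrase "using Wisepill openings as an example" from section 12.1.
2. List chart-review management actions as the provider endpoint, estimated by arm with a 95% confidence interval.
3. Make TFV-DP, viral load and self-report secondary, reported as estimates with confidence intervals and no significance claim.
4. Take exit interviews and focus groups out of the endpoint and out of the adherence hypothesis (sections 5.3 and 12.3), and place them under explanatory and feasibility analyses.
5. State in section 12.1 that the power figure assumes Wisepill change scores have the Aim 1 self-report SD of 11.42. That SD describes adherence levels on another measure, and the documents give none for Wisepill.

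**Cost.** Protocol wording only; data collection and sample size do not change. A difference seen only in TFV-DP, viral load or self-report could no longer be called the primary result, and the power figure becomes openly assumption-based. The alternative of keeping four primary measures with Bonferroni costs about 18 points of power (79.3% to 60.9%).
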